**A Feasibility Study Evaluating Flexitouch® Plus with Novel
Simultaneous Therapy Cycle Software in Patients with
Unilateral Breast Cancer-Related Lymphedema (BCRL)**

**Protocol Number: 4070
NCT04073823**

**May 15, 2019
Protocol Version 2.0**

Investigator Signature

Protocol Title: A Feasibility Study Evaluating Flexitouch Plus with Novel Simultaneous Therapy Cycle Software in Patients with Unilateral Breast Cancer-Related Lymphedema (BCRL)

Protocol Number: 4070

I confirm that I have read this protocol. I will comply with the protocol and the principles of Good Clinical Practices (GCP), institutional research policies and procedures, and other appropriate regulatory requirements.

Site Principal Investigator Name (Print)

Site Principal Investigator Signature

Date

SYNOPSIS

Study Title	A Feasibility Study Evaluating Flexitouch Plus with Novel Simultaneous Therapy Cycle Software in Patients with Unilateral Breast Cancer-Related Lymphedema (BCRL)
Protocol Date	15 May 2019
Protocol Version	2.0
Protocol Number	4070
Name of Sponsor	Tactile Medical
Investigational Product	Flexitouch Plus (FT) with Novel Simultaneous Therapy Cycle Software (FT-SW)
Study Objective	To demonstrate the treatment equivalency of the Flexitouch Plus with novel simultaneous therapy cycle software and the standard Flexitouch Plus in patients with unilateral BCRL.
Endpoints	To compare the effects of the Flexitouch Plus (FT) to Flexitouch Plus with novel simultaneous therapy cycle software (FT-SW) in unilateral BCRL patients after one treatment by evaluating: 
 Flow of lymph in the affected and contralateral limb using near infrared-fluorescence (NIRF) imaging Swelling in the affected and contralateral limb as assessed by: 
 Perometry (LymphaTech 3D Scanner) Local tissue water (MoistureMeterD) Skin changes 
 Skin thickness (Ultrasound) Safety
Study Design	This is a prospective, randomized, two-arm feasibility study.
Treatments	Eligible patients will be randomized to receive one of the following treatments: 
 Flexitouch Plus (FT) Flexitouch Plus with Novel Simultaneous Therapy Cycle Software (FT-SW) The compression treatment will be conducted on the affected limb.
Inclusion/Exclusion	
Inclusion Criteria:
 
 Female 18 years of age or older Diagnosis of unilateral breast cancer-related lymphedema Stage I or early Stage II lymphedema without severe fibrosis at the time of enrollment ≥ 5% volume difference between affected and unaffected arm as verified via perometry (LymphaTech 3D scanner) Willing and able to give informed consent Willing and able to comply with the study protocol requirements and all study-related visit requirements 
Exclusion Criteria:
 
 In-home use of pneumatic compression device (PCD) within previous 3 months

	
 2. Therapist or self-administered manual lymph drainage (MLD) within previous 1 week 3. Mastectomy or lymph node removal on side without lymphedema 4. Bilateral lymphedema 5. Heart failure (acute pulmonary edema, decompensated acute heart failure) 6. Acute venous disease (acute thrombophlebitis, acute deep venous thrombosis, acute pulmonary embolism) 7. Active skin or limb infection/inflammatory disease (acute cellulitis, other uncontrolled skin or untreated inflammatory skin disease) on the arms or trunk 8. Active cancer (cancer that is currently under treatment, but not yet in remission) 9. Poorly controlled kidney disease (glomerular filtration rate < 30 mls per minute), hypoproteinemia, pulmonary hypertension, hypothyroidism, cyclic edema, or Munchausen Syndrome 10. Body Mass Index (BMI) >50 11. Any circumstance where increased lymphatic or venous return is undesirable 12. Currently pregnant or trying to become pregnant 13. Allergy to iodine
Treatment Duration	
A single treatment lasting:
 
 • FT-SW: Approximately 40 minutes OR • FT: Approximately 60 minutes
Number Planned	20 subjects randomized (minimum of 10 in each arm) with replacement of up to 5 early withdrawals.

TABLE OF CONTENTS

1.0	Contact Information	7
1.1	Sponsor Contact Information.....	7
1.2	Principal Investigator Information.....	7
1.3	Clinical Investigator Information	7
2.0	Abbreviations	8
3.0	Introduction.....	10
3.1	Background and Rationale.....	10
3.2	Device Description	10
4.0	Study Objective.....	13
5.0	Study Design.....	13
5.1	Endpoints	13
5.2	Subject Selection	14
5.3	Point of Enrollment and Randomization	15
5.4	Treatment Assignment and Duration.....	15
5.5	Study Timeline	15
6.0	Study Assessments.....	15
6.1	Screening/Baseline	16
6.2	Randomization.....	16

1.3 Clinical Investigator Information

The sponsor will maintain a document with contact information for all investigators participating in the study. The information maintained will include full name, addresses, telephone, and, if available, email addresses and mobile phone numbers for the site principal investigators and Institutional Review Board (IRB) chairperson.

2.0 Abbreviations

Abbreviation	Term
AE	Adverse Event
BCRL	Breast Cancer-Related Lymphedema
BMI	Body Mass Index
CFR	Code of Federal Regulations
CMI	Center for Molecular Imaging
CRA	Clinical Research Associate
CRF	Case Report Form
CTA	Clinical Trial Agreement
DCF	Data Clarification Form
ESAS-R	Edmonton Symptom Assessment System
EDC	Electronic Data Capture
FDA	Food and Drug Administration
FT	Flexitouch Plus
FT-SW	Flexitouch Plus with Novel Simultaneous Therapy Cycle Software
GCP	Good Clinical Practice
ICG	Indocyanine Green
IMM	The Brown Foundation Institute of Molecular Medicine
IND	Investigational New Drug
IRB	Institutional Review Board
LTW	Local Tissue Water
PCD	Pneumatic Compression Device
mg/kg	milligram/kilogram
MLD	Manual Lymphatic Drainage
mm	millimeter
MMD	MoistureMeterD™
NIRF	Near Infrared-Fluorescence
NSR	Nonsignificant Risk
PI	Principal Investigator
SAE	Serious Adverse Events
SAP	Statistical Analysis Plan

Abbreviation	Term
TDC	Tissue Dielectric Constant
US	Ultrasound
USA	United States of America
HCPGS	Healthcare Common Procedure Coding System
UADE	Unanticipated Adverse Device Effect
µg	microgram
µg/ml	micrograms/millimeter
UTHealth	University of Texas Health Science Center at Houston

3.0 Introduction

3.1 Background and Rationale

Lymphedema is a chronic debilitating disease marked by accumulation of protein rich fluid in the interstitium of the skin (1). This insufficiency in the lymphatic system leads to limb edema in early stages and progresses to thickened skin or fibrosis over time. As a result, persons afflicted with lymphedema are prone to develop impaired extremity function, recurrent episodes of soft tissue inflammation and infection, lymphorrhea, unsatisfactory cosmesis, and a variety of psychological and social issues (2).

Lymphedema may be inherited (primary) or caused by injury to the lymphatic vessels (secondary). While the exact cause of primary lymphedema is unknown, it generally occurs due to congenital malformations with the onset of symptoms presenting at birth, during puberty, or well into adulthood. Secondary lymphedema typically results from trauma to the lymphatic system, surgery, radiation therapy, obesity, and chronic venous insufficiency (3-4). Breast Cancer-Related Lymphedema (BCRL) is a common complication from breast cancer treatment, with reported frequencies ranging from 6% to 65% (5).

There is currently no cure for lymphedema, thus treatment focuses on symptom management and improved patient-reported outcomes. Using a multimodal approach, accepted interventions include: limb elevation, manual lymphatic drainage, compression therapy, skin hygiene, and in very severe cases, lymphatic exchange (6). Pneumatic Compression Devices (PCDs) are a fairly recent addition to the armamentarium clinicians offer patients in the treatment of lymphedema. Studies have demonstrated continual use of PCDs is associated with a significant patient-reported improvement in overall symptoms, decreased limb-girth, decreased limb volume, increased elasticity of tissues, and fewer episodes of infection (7-10).

The efficacy of PCD therapy depends on the applied force (pressure) mobilizing stagnant edema fluid, time of compression to move fluid to the root of the limb, and elasticity of skin and subcutaneous tissue. Thus, adherence to prescribed, at-home self-care is a critical factor in the treatment of lymphedema (11-12). One of the most robust findings in adherence literature concerns aspects of the therapy itself – the more complex and complicated a therapeutic regimen is (e.g., treatment duration), the less likely patients are to adhere to all aspects of prescribed care (12).

To address non-adherence, the FT was updated with the novel simultaneous therapy software to shorten treatment time. Currently, the FT takes approximately 1 hour of treatment to provide clearing of the trunk, chest, and arm. With the novel simultaneous therapy cycle software engaged, the device will run two simultaneous therapy cycles. Thus, the simultaneous therapy cycle program will provide the same number therapy cycles as a traditional FT while reducing treatment time.

The purpose of this study is to demonstrate equivalency in treatment effect between the novel simultaneous therapy cycle software and the standard FT.

3.2 Device Description

3.2.1 Flexitouch Plus (FT)

The FT (Tactile Medical™, Minneapolis, MN, USA) is a segmental, programmable, gradient advanced pneumatic compression device cleared for market in the USA (K170216, HCPCS code E0652). The device stimulates the lymphatic system by directing and moving excess fluid from an impaired lymphatic region to healthy regions where fluid can be absorbed and processed naturally by the body.

The FT consists of two primary components: a controller unit and garments. The controller unit has connector outlets for garment hoses to plug into such that air can pass through the hoses and deliver treatment through sequential inflation and deflation of air chambers within the garments. The garments are constructed of nylon and have 27-32 chambers, depending upon garment size. The pressure setting is variable between “decreased,” “normal,” and “increased.”

The device is intended to provide Manual Lymphatic Drainage (MLD) therapy for approximately 1 hour treatment duration. Indications for use include lymphedema, primary lymphedema, post-mastectomy edema, edema following trauma and sports injuries, post immobilization edema, venous insufficiency, reducing wound healing time, and treatment and assistance in healing stasis dermatitis, venous stasis ulcers, or arterial and diabetic leg ulcers.

3.2.2 Flexitouch Plus with Novel Simultaneous Therapy Cycle Software (FT-SW)

The investigational device utilized in this study is the FT-SW. The software was developed for use with the current-generation FT and allows the device to run two simultaneous waves of therapy. As shown in Figure 1, the novel software provides the same number of therapy cycles as a traditional FT, however 2 simultaneous waves are applied instead of one. Application of these simultaneous waves results in a reduction in treatment time. The intended use, indications, and garments for the FT-SW are identical to the FDA cleared FT system.

The FT-SW will be labeled, “CAUTION – Investigational Device, Limited by Federal Law to Investigational Use” and will have the unique 10 character serial number.

[figure not shown]

Figure 1. FT and FT-SW

3.2.3 NIRF Imaging

The investigational imaging techniques of near-infrared fluorescence (NIRF) are focused on addressing unmet clinical diagnostic needs in lymphatic imaging through point of care, non-radioactive, clinical imaging diagnostic platform based on image intensifier technology. NIRF imaging has been used under the investigational new drug (IND) experience by the

Principal Investigator (PI) to map lymphatic structure and visualize lymphatic function in hundreds of patients without adverse effects. This method of imaging has shown efficacy in detecting impaired lymphatic function with dermal backflow, defined as abnormal fluorescent signal observed in networks of lymphatic capillaries and/or in the extravascular space, presenting as one of the earliest signs of lymphedema onset (13-15).

NIRF lymphatic imaging provides real-time imaging of the lymphatic anatomy and its function. Following intradermal injections of 25 micrograms of indocyanine green (ICG) in 0.1 cc sterile saline, a dim laser diode light of 785 nm is illuminated on the tissue surface. The light penetrates the tissues and excites the ICG and the resultant fluorescence emanates from tissues and is collected using an intensified camera system.

4.0 Study Objective

The objective of the study is to demonstrate equivalency in treatment effect, as determined by objective measurements, between the novel simultaneous therapy cycle software and the FDA-cleared FT.

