5.1 Endpoints

To compare the effects of FT to FT-SW in BCRL patients after one treatment based upon:

- Lymphatic activation in the affected and contralateral limb using the investigational technique of near infrared-fluorescent (NIRF) imaging
- Swelling in the affected and contralateral limb as assessed using:
 - Perometry (LymphaTech 3D Scanner)
 - Local tissue water content (MoistureMeterD)
- Skin changes on the affected and contralateral limb as assessed by:
 - Skin thickness (Ultrasound)
- Safety

Table 1. Outcome Measures

Endpoint	Outcome Measure
Lymphatic activation	
 Proportion of subjects who show an increase in the number of functional vessels and/or area of dermal backflow per NIRF imaging of the affected and contralateral arm when comparing post-treatment values to pre-treatment values Proportion of subjects who show an increase of lymphatic propulsion events immediately after treatment
Changes in Swelling	
 Proportion of subjects who show a decrease in arm perometry (limb volume) when comparing post-treatment values to pre-treatment values for the affected and contralateral arm Proportion of subjects who show a decrease in local tissue water at target sites when comparing post-treatment values to pre-treatment values for the affected side Mean change in perometry and local tissue water post-treatment will be compared for all sites
Skin Changes	
 Proportion of subjects who show a decrease in skin thickness at target site when comparing post-treatment values to pre-treatment values for the affected side Mean change in skin thickness post-treatment will be compared for all sites
Safety	
 Adverse events will be presented in data listings

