16.0 Statistical Methods

For continuous variables, descriptive statistics will include the number of subjects (n), mean, standard deviation, median, inter-quartile range, minimum, and maximum, based upon subjects with reported data for the variable being analyzed.

Frequencies (numerator and denominator), percentages, and 95% confidence intervals will be displayed for categorical data. Percentages by categories will be based on the number of subjects with no missing (unreported) data for the specific variable being analyzed and the count of the patients for each individual level of the categorical variable (the level specific numerators). Percentages will add up to 100%, unless otherwise indicated.

There are no plans to impute missing data and there are no plans to explicitly report missing data (counts and/or percentages) in the tables for all variables as part of the planned study report content. Variations in the reported sample sizes within and/or between relevant tables can be used to ascertain insights into unreported data. In some cases, unreported data may be the result of it not being clinically relevant to a particular patient or may represent expected data that was not collected. Selected analyses pertaining to unreported and/or missing data may be discussed and considered as future findings warrant.

The feasibility nature of the study suggests that the statistical focus will be on estimation and hypothesis generation. Thus, formal statistical tests of hypotheses are not planned.

All data processing, summarization, and analyses will be performed using R Version 3.54.0 or higher.

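### The sole objective is to demonstrate equivalency, but the plan has no margin, decision rule or FT-SW minus FT interval, and 10 per arm supports estimation only

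*Combined protocol and SAP*

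**What the plan says.** The objective appears three times, each time as a demonstration of equivalence:

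- Synopsis, Study Objective: "To demonstrate the treatment equivalency of the Flexitouch Plus with novel simultaneous therapy cycle software and the standard Flexitouch Plus".
- Section 3.1: "The purpose of this study is to demonstrate equivalency in treatment effect between the novel simultaneous therapy cycle software and the standard FT".
- Section 4.0: "The objective of the study is to demonstrate equivalency in treatment effect, as determined by objective measurements".

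The analysis section takes a different position. Section 16.0 says "the statistical focus will be on estimation and hypothesis generation. Thus, formal statistical tests of hypotheses are not planned". Its outputs are as follows:

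- Categorical data: "Frequencies (numerator and denominator), percentages, and 95% confidence intervals will be displayed for categorical data". It does not say whether these intervals are for each arm or for the difference between arms.
- Continuous data: "descriptive statistics will include the number of subjects (n), mean, standard deviation, median, inter-quartile range, minimum, and maximum". No interval is listed.

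Table 1 in Section 5.1 lists responder proportions and adds "Mean change in perometry and local tissue water post-treatment will be compared for all sites", with similar wording for skin thickness. It names no contrast or method. The synopsis gives the sample size as "20 subjects randomized (minimum of 10 in each arm) with replacement of up to 5 early withdrawals", with no rationale. Section 17.0 says the data are meant for product development and marketing claims, will be kept on file, and are not planned for publication.

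**The concern.** A claim of equivalence needs three things fixed in advance: the outcome on which it is judged, the largest difference that would still count as equivalent, and a rule linking the interval for the difference to that margin. The plan has none of them. It also does not define the between-arm difference itself, so even the more modest aim in Section 16.0 is incompletely specified.

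The documents do not say that similar-looking summaries will be called equivalent. They offer no other route from the planned output to the stated objective, however. In a small study, similar observed results are weak evidence of similarity, because wide intervals are compatible with large differences in either direction. The intended marketing use makes the wording matter. With no publication planned, the protocol text is one of the few constraints on how the results are described.

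**Working it through.** **Is there a figure to reproduce?** No. The sample size of 20 comes with no alpha, power, SD, response rate or margin, so there is no arithmetic error to find. What can be checked is the precision that 10 per arm gives.

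**Inputs from the documents:** 10 subjects per arm (synopsis, Number Planned) and the 95% confidence level (Section 16.0). The documents give no SD, response rates or margins. Results for means are therefore in SD units, proportions are shown over a range of observed rates, and every margin below is an assumption.

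**1. Difference in responder proportions, identical observed rates (Newcombe interval).** The Wilson limits for x/n are

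[p + z²/2n ± z√(p(1−p)/n + z²/4n²)] / (1 + z²/n), with z = 1.96 and n = 10.

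With Wilson limits (l, u) in each arm and equal observed p, the half-width for the difference is √[(p − l)² + (u − p)²].

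- At 5/10 the Wilson limits are 0.237 and 0.763. The half-width is √(0.263² + 0.263²) = 0.373.
- At 10/10 the limits are 0.722 and 1. The half-width is 1 − 0.722 = 0.278.

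| Responders in each arm | 95% half-width (percentage points) |
|---|---|
| 5/10 | 37 |
| 6/10 | 37 |
| 7/10 | 36 |
| 8/10 | 34 |
| 9/10 | 32 |
| 10/10 | 28 |

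**2. Difference in means.** Half-width = t(0.975, 18 df) × SD × √(2/10) = 2.101 × 0.447 × SD = 0.94 SD. The documents give no SD and no clinically important difference, so they do not allow a judgement on whether 0.94 SD is large.

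**3. Illustration: what an equivalence test could do.** Assume two one-sided 5% t-tests, which amounts to requiring the 90% interval to lie inside ± the margin. Assume also a true difference of exactly zero, the most favourable case. Power was integrated numerically over the distribution of the pooled variance.

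| Assumed margin | Power at 10 per arm | Smallest n per arm for 80% power |
|---|---|---|
| 0.5 SD | 0.1% | 70 (80.6%) |
| 0.75 SD | 8% | 32 (81.4%) |
| 1.0 SD | 39% | 18 (80.5%) |

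At 10 per arm, 80% power is reached only at a margin of about 1.36 SD.

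For proportions, an assumed 20-point margin could not be met by any result. Even 10/10 against 10/10 gives a 90% interval of ±21 points. A normal-approximation formula puts the size needed for that margin, at 80% power and one-sided 5%, at 103 per arm if both true rates are 60% and 39 per arm if both are 90%.

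**4. Number of comparisons.** If all sites means sites A to C on both arms with both probes, the mean differences are: volume, 2 arms = 2; local tissue water, 3 sites × 2 probes × 2 arms = 12; skin thickness, 3 sites × 2 arms = 6. The total is 20. The responder-proportion differences come on top of that.

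**The case against.** The strongest reply is that this is a feasibility study by title and design, and that Section 16.0 openly disclaims testing. On that view the objective is one over-ambitious sentence. Correcting it changes nothing in allocation, treatment, assessment or patient numbers, so the point is less than essential. It is true that the analysis section is appropriate and that the remedy is light. But the sentence appears in three places and is the only objective the study has, and a disclaimer in Section 16.0 does not correct it.

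A second reply is that between-arm information is not absent. The protocol says the treatments will be compared, categorical intervals are planned, and a reader could derive a difference and a t interval from the reported n, mean and SD. This is fair: the contrast is under-specified and the output is not empty. The lack of a margin and decision rule still means that no such derived interval could settle the objective.

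Third, the power figures rest on assumed margins and prove no defect in themselves. They are illustrative, and the mismatch stands without them.

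Finally, the precision figures assume 10 complete observations per arm. Section 8.11 leaves ultrasound sites with blurred borders unmeasured and Section 16.0 plans no imputation, so fewer than 10 skin-thickness values per arm are possible. The intervals would then tend to be wider in SD units than shown, which strengthens the point.

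**Conclusion.** The concern holds. The plan states a confirmatory equivalence objective in three places and provides an analysis that cannot answer it: no margin, no decision rule, no primary outcome, no specified FT-SW minus FT interval, and no interval of any kind listed for continuous outcomes. This should be corrected before the study reports.

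On size: with 10 per arm and identical observed results, a 95% interval leaves open a difference of about 28 to 37 points in responder rate in either direction. For means the half-width is 0.94 SD whatever the observed difference. These figures need only the planned sample size, complete data and, for proportions, equal observed rates. The equivalence power and resizing figures depend in addition on margins that the documents do not supply.

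**What to change.** **Recommended.**

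1. In the synopsis, Section 3.1 and Section 4.0, replace the objective with: *to estimate the difference in acute treatment effect between FT-SW and FT*.
2. In Section 16.0, state that each efficacy outcome in Table 1 will be reported as FT-SW minus FT with a 95% confidence interval, for example Newcombe for proportions and t-based for means. State also whether the categorical intervals already planned are for each arm.
3. Add that these intervals are descriptive and not adjusted for multiplicity, and that similarity of observed results will not be described as equivalence.

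The cost is protocol wording and one extra column per table, with no added patients. The downside is a weaker claim and many intervals to be read descriptively: about 20 mean differences on the reading above, plus the responder-proportion differences.

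**If the sponsor wants to keep the equivalence objective.** Name one primary outcome, justify a margin for it, state the decision rule and resize the study. Illustratively, 80% power with truly identical arms needs 18 to 70 per arm for assumed margins of 1.0 to 0.5 SD on a mean. An assumed 20-point margin on a proportion needs about 39 to 103 per arm, for true rates of 90% down to 60%.
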